7.5.1 Drop out Criteria

Subjects are classified as drop-outs if they do not complete the study protocol through the final assessment (week 16) for any reason. Specific drop-out criteria include:

- Non-adherence to intervention: Failure to attend >3 consecutive structured exercise sessions (intervention arm) or $<85\%$ of total planned exercise sessions; failure to attend ≥ 2 intergenerational activity sessions or $<85\%$ overall attendance for SHP phase.
- Development of exclusion criteria during study: New onset of disability, suspected/confirmed dementia, depression (GDS-15 score indicating moderate-severe depression requiring intervention), total immobility, uncontrolled chronic disease, or hemodynamic instability.
- Acute illness or clinical worsening: Occurrence of acute conditions (e.g., pneumonia, acute arthritis with VAS $>6/10$, acute stroke, acute myocardial infarction, uncontrolled hypertension $\geq 180/100$ mmHg, acute COPD exacerbation) requiring hospitalization or prohibiting continuation.
- Adverse events suspected related to intervention: Intolerable or serious symptoms (e.g., persistent severe fatigue, muscle pain, dizziness, fall during exercise, significant emotional distress during intergenerational activities) leading to investigator decision for withdrawal.
- Voluntary withdrawal: Subject (or orphanage representative for children) requests discontinuation for any personal reason (e.g., lack of time, loss of motivation, transportation difficulties).
- Loss to follow-up: Inability to contact subject despite ≥ 3 attempts via phone/WhatsApp over 2 weeks, or permanent relocation outside study area.
- Death: Any mortality during study period (reported immediately as serious adverse event).

All drop-outs are documented in detail (date, reason, last completed assessment/procedure) on the case report form and in the trial master file.

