1. INTRODUCTION AND RATIONALE

Indonesia is a country with an ageing population, with older adults comprising approximately 12% of the total population and a current life expectancy of 72.39 years. The World Health Organization (WHO) has introduced the concept of healthy aging, which emphasizes the importance of maintaining functional ability and intrinsic capacity in older adults to enable them to remain healthy and independent. Impairment of functional ability can lead to disability, which has a greater impact than multimorbidity, underscoring the need for early intervention.

One important early condition in older adults that requires particular attention is physio-cognitive decline syndrome (PCDS), which is defined as the coexistence of physical functional decline (i.e., reduced gait speed or handgrip strength, in the absence of disability) and cognitive decline (without dementia). PCDS increases the risk of frailty and deterioration in quality of life; however, it remains a potentially reversible condition. Multidomain interventions, such as physical and cognitive exercise, have been shown to improve this condition.

One important biomarker of brain neuroplasticity is mature brain-derived neurotrophic factor (mBDNF), which reflects the muscle–brain axis. Social isolation, loneliness, and depression further exacerbate PCDS. Therefore, social interventions such as social heterochronic parabiosis (SHP)—defined as direct interactions between older adults and younger generations, particularly children or adolescents—may represent a promising strategy to improve cognitive function. Intergenerational activities have been shown to enhance mental health, cognitive function, and physical performance in healthy older adults.

To date, no studies have specifically described the model and/or role of SHP-based interventions in improving physical and cognitive decline among older adults with PCDS. This study utilizes educational materials with the potential to facilitate SHP-based interventions in Indonesia, namely the “Ayo Minum Air” (AMIR) campaign developed by the Indonesian Hydration Working Group (IHWG). These educational materials serve as media to facilitate direct interactions between older adults and children (e.g., illustrated comics, exercise videos, and related materials), which are essential components of SHP-based interventions.

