3. STUDY DESIGN

This is a single-center, randomized, open-label (unblinded), parallel-group controlled clinical trial evaluating the efficacy of a sequential multimodal intervention (structured physical exercise followed by SHP-based intergenerational activities) compared to nutritional education alone in community-dwelling elderly aged 60–75 years with physio-cognitive decline syndrome (PCDS).

The study duration per participant is 16 weeks, consisting of:

- Baseline assessment (week 0)
- Intervention period: 12 weeks of chair-exercise + 4 weeks of intergenerational activities (intervention arm) or continued education (control arm)
- Intermediate assessment (end of week 12)
- Final assessment (end of week 16)

Participants are randomized in a 1:1 ratio into two arms:

- Intervention arm (n=50): Nutritional education + 12 weeks structured chair-based exercise (PEROSI protocol, progressive frequency from 1 to 3 sessions/week, 60 minutes/session, supervised online) followed sequentially by 4 weeks SHP-based intergenerational activities (8 sessions, 2x/week, 45 minutes/session, paired 1:1 elderly-child using AMIR educational materials at selected orphanages).
- Control arm (n=50): Nutritional education only (2 personalized dietitian tele-conferences at weeks 1 and 11; 5 educational e-flyers at weeks 3, 5, 7, 13, and 15).

Randomization is computer-generated using permuted block randomization (block size 4), stratified if necessary, with allocation concealment managed by an independent third party. Blinding of participants and instructors is not feasible due to the nature of the behavioral interventions; however, outcome assessors for laboratory analyses (mBDNF) are blinded to group allocation where possible.

The trial follows intention-to-treat principles with per-protocol sensitivity analysis. Recruitment targets consecutive eligible elderly from community programs under the School of Medicine and Health Sciences at Atma Jaya Catholic University of Indonesia and the Archdiocese of Jakarta. Child participants (aged 5–8 years, n=50) are recruited from cooperating orphanages exclusively for the intervention arm.

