5. TREATMENT OF SUBJECTS

Subjects will be randomly assigned to one of two groups: structured physical exercise followed by a social heterochronic parabiosis (SHP)-based intervention (intervention group) or usual care only (control group). Randomization will be computer-generated using a block-permuted randomization method with variable block sizes of four. The randomization list will be held by an independent third party (staff of the Department of Internal Medicine, School of Medicine and Health Sciences, Atma Jaya Catholic University of Indonesia) who is not involved in the research team. Both the investigators and the participants will be blinded to group allocation.

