7.2 Randomization, blinding, and treatment allocation

Randomization is performed after screening and baseline assessments using computer-generated permuted block randomization (block size 4). Allocation is managed by an independent third party (staff from the Department of Internal Medicine, School of Medicine and

Health Sciences at Atma Jaya Catholic University of Indonesia), not involved in the study. Sequence is concealed until assignment. Participants are allocated 1:1 to intervention or control arm.

Due to the behavioral nature of the intervention, blinding of participants, instructors, and research team is not possible (open-label design). However, laboratory analysts for mBDNF measurement are blinded to group allocation. Outcome assessors for physical measurements (grip strength, gait speed) are trained for consistency (inter-rater reliability tested with Kappa statistic).

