7.5 Withdrawal of individual subjects

Participants (elderly or children via orphanage representative) may withdraw voluntarily at any time without providing reasons and without impact on routine care or relationship with researchers. Withdrawal is documented but no further study procedures performed unless consented for final assessment.

Investigator-initiated withdrawal occurs for:

- Development of exclusion criteria (e.g., new disability, dementia suspicion, uncontrolled chronic disease).
- Acute illness requiring hospitalization or prohibiting continuation (e.g., pneumonia, acute stroke, uncontrolled hypertension).
- Non-adherence (>3 consecutive missed exercise sessions or <85% overall intervention completion).
- Intolerable adverse events suspected related to intervention.

Withdrawn participants are encouraged to complete safety follow-up and/or final assessments for intention-to-treat analysis. All withdrawals are fully documented (reason, date, partial data

collected) and reported to Ethics Committee if related to safety. No replacement of withdrawn subjects.

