7.7 Follow-up of subjects withdrawn from treatment

Withdrawn subjects are encouraged to complete final assessments for intention-to-treat analysis where possible.

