9. STATISTICAL ANALYSIS

All collected data will be initially recorded on research case report forms (CRFs) and subsequently transferred to secure electronic storage for data cleaning, coding, and verification. Descriptive data and analytical results will be presented in narrative text, tables, or figures as appropriate.

Normality of data distribution will be assessed using the Kolmogorov-Smirnov or Shapiro-Wilk test ($p > 0.05$ indicates normal distribution). Normally distributed continuous data will be presented as mean \pm standard deviation (SD); non-normally distributed data as median with minimum-maximum range. Categorical data will be presented as frequencies and percentages. Statistical significance will be set at $p < 0.05$. All analyses will be performed using SPSS version 20 software.

Primary analyses will be conducted on the per-protocol (PP) population, excluding drop-out subjects. Between-group comparisons of changes in study outcomes (hand grip strength, gait speed, MoCA-Ina score, serum mBDNF levels, and health-related quality of life) will use unpaired t-tests (parametric) or Mann-Whitney U tests (non-parametric), selected based on normality test results.

Correlations between serum mBDNF levels and MoCA-Ina score, hand grip strength, and gait speed will be evaluated using Pearson correlation (for normally distributed variables) or Spearman correlation (for non-normally distributed variables), according to normality assessment of each variable.

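### Section 9 makes per-protocol the primary analysis and drops subjects for outcome-related post-randomisation events, against the intention-to-treat plan in Sections 3, 7.5 and 7.7

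*Combined protocol and SAP*

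**What the plan says.** Two analysis populations are named as the main one. Section 3 (Study Design): "The trial follows intention-to-treat principles with per-protocol sensitivity analysis". Section 9 (Statistical Analysis): "Primary analyses will be conducted on the per-protocol (PP) population, excluding drop-out subjects". Section 9 describes no intention-to-treat analysis.

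Data for one are nevertheless sought. Section 7.5: "Withdrawn participants are encouraged to complete safety follow-up and/or final assessments for intention-to-treat analysis". Section 7.7: "Withdrawn subjects are encouraged to complete final assessments for intention-to-treat analysis where possible".

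Section 7.5.1 decides who counts as a drop-out. Its lead sentence ties the term to not completing the protocol through week 16. A list of specific criteria follows. Under exclusion criteria that develop on study it includes "depression (GDS-15 score indicating moderate-severe depression requiring intervention", beside new disability and suspected or confirmed dementia. It also lists non-adherence: missing more than 3 exercise sessions in a row, attending fewer than 85% of exercise sessions, missing 2 or more intergenerational (SHP) sessions, or attending less than 85% of that phase.

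On blinding, Section 7.2 says "blinding of participants, instructors, and research team is not possible (open-label design", and Section 3 also calls the trial open-label. Section 5 says the opposite: "Both the investigators and the participants will be blinded to group allocation". For supervised exercise and orphanage visits, open-label is the credible reading.

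**The concern.** The plan gives two incompatible answers to who is in the primary analysis, and nothing reconciles them. If Section 9 is followed, participants leave the comparison because of things that happen after randomisation, some of which the protocol itself connects with outcome.

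Depression is a clear case. Section 1 states: "Social isolation, loneliness, and depression further exacerbate PCDS". Section 4.2 defines PCDS by gait speed, grip strength and MoCA-Ina score, which are three of the five outcomes that Section 9 compares between groups. A fourth, SF-12, has a mental component. These are secondary endpoints. Among the main endpoints, frailty is linked through the exhaustion, weakness and slowness items of the CHS criteria (7.3.4); the documents draw no direct link from depression to mBDNF.

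The judgement that depression requires intervention is made by an unblinded team. The blinded mBDNF assay protects that measurement, but not the choice of whose samples are compared. The 15% drop-out allowance in 7.6 protects numbers, not comparability. An unresolved choice between two primary populations could also be settled after results are seen.

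**Working it through.** **Plan's own figure.** Section 4.5 gives a largest requirement of 42 per group, and 7.6 allows up to 15% drop-out. 42 / (1 − 0.15) = 49.4, rounded up to 50 per group, as stated. The 42 itself cannot be rebuilt because no effect sizes or SDs are given. By inversion (two-sided 5%, 80% power), the detectable difference is (1.96 + 0.84) × √(2/42) = 0.61 SD.

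**How the texts combine.**

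| Step | Section | Result |
|---|---|---|
| Moderate-severe depression needing intervention develops on study | 7.5.1 | Listed drop-out criterion |
| Development of exclusion criteria | 7.5 | Investigator-initiated withdrawal |
| Withdrawn participant invited to final assessment | 7.5, 7.7 | Week-16 data may exist, meant for intention-to-treat |
| Primary analysis | 9 | Drop-outs excluded; those data are unused |

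**When depression would be detected.** After baseline, GDS-15 is scheduled at weeks 12 and 16 (7.4). Someone first scoring high at week 16 has already completed the protocol and, on the lead sentence of 7.5.1, is not a drop-out. The ground therefore concerns mainly participants identified at week 12 or clinically between visits.

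**Attendance rules.** Exercise sessions (5.1): 1×2 + 2×4 + 3×6 = 28. 85% of 28 = 23.8, so at least 24 must be attended, and missing 5 makes a drop-out. SHP sessions: 85% of 8 = 6.8, so at least 7 must be attended, and missing 2 makes a drop-out. Controls have neither kind of session, so these exclusions fall on one arm by construction.

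**Size for depression alone (illustration).** Let k be the net extra removals in one arm of 50, and δ how much worse those removed score than those retained. Shift in the group difference = (k/50) × δ. Both k and δ are assumed. Type I error is for a two-sample t-test, (50 − k) against 50, SD 1, with a true difference equal to the shift (noncentral t).

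| k | δ (SD) | Shift (SD) | Type I error |
|---|---|---|---|
| 1 | 0.5 | 0.01 | 5.03% |
| 2 | 1 | 0.04 | 5.44% |
| 3 | 1 | 0.06 | 5.98% |

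Against the detectable 0.61 SD, the shift runs from 0.01/0.61 = 1.6% to 0.06/0.61 = 9.8%. Equal and similar removals in both arms cancel.

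**Outer limit on numbers.** 0.15 × 50 = 7.5, so about 7 per arm for all grounds together; depression can be only part of that.

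**The case against.** Four points can be made for the plan.

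*Depression is a minor route.* People with depression are excluded at entry (4.3), the ground can arise in either arm, and its effect is small even under unfavourable assumptions. This stands. The attendance rules probably remove more people and do so asymmetrically. It is a reason to state the conflict for all drop-out grounds, with depression as one example.

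*The lead sentence of 7.5.1 limits drop-out to those who do not reach week 16.* This stands in part. A reader might infer that anyone who becomes depressed is excluded even when first identified at the final visit; the lead sentence does not support that. But the list presents each ground as a criterion in itself, and 7.5 makes development of an exclusion criterion a reason for withdrawal. A participant withdrawn at week 12 who returns at week 16 could be classed either way.

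*The criterion is narrow.* This stands. A reader might take a GDS-15 score of 5 or more, which 7.3.9 says suggests depression, as the trigger. The documents do not say so: 7.5.1 asks for a moderate-severe score that requires intervention, and gives no score for moderate-severe.

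*Intention-to-treat is not free.* This stands. Final assessments of withdrawn participants are only encouraged, and Section 9 has no method for missing week-16 values, so changing the population label alone would not be enough.

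**Conclusion.** The conflict is real and should be resolved before data are analysed. Section 9 contradicts Sections 3, 7.5 and 7.7 and, followed as written, excludes participants on outcome-related grounds after randomisation in an open-label trial.

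For depression alone the effect is probably small: a shift of 0.01 to 0.06 SD and type I error of 5.0% to 6.0%, resting entirely on assumed removals (net 1 to 3 of 50) and assumed outcomes (0.5 to 1 SD worse). The documents give no GDS-15 distribution, so the number affected cannot be estimated. The other grounds are not quantified here, because the documents do not split expected drop-out by reason.

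A reader might infer that the exclusions would favour the intervention. The documents do not support a direction: removing worse-scoring participants from an arm flatters that arm, and nothing says which arm would lose more to depression. The attendance rules do act on one arm only, but how poor attenders would have scored is not known.

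**What to change.** In Section 9, make the primary analysis intention-to-treat: all randomised participants, analysed as randomised, including week-16 data from withdrawn participants who consent. Keep per-protocol as the sensitivity analysis, as Section 3 has it. Add a stated approach to missing week-16 values.

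In 7.5.1, state that stopping the intervention for depression or any other listed ground does not by itself remove a participant from the week-16 assessment or from the primary analysis. As a minor clarification, give the GDS-15 score meant by moderate-severe.

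**Cost.** No new visits or measurements: 7.5 and 7.7 already seek the final assessments. There is a little more analysis work for the missing-data method, and the effect estimate may be diluted by participants who stopped early. There is some room for that. With 50 per group and complete data, 80% power needs (1.96 + 0.84) × √(2/50) = 0.56 SD, so the implied 0.61 SD could shrink by about 8% (1 − 0.56/0.61) before power falls below 80%. Missing week-16 values would reduce that margin.

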7.6 Replacement of individual subjects after drop out

Dropped-out subjects are not replaced. The initial sample size calculation (minimum 100 elderly participants, 50 per group) incorporates an anticipated drop-out rate of up to 15% (based on similar community-based geriatric intervention studies) to ensure sufficient statistical power for primary endpoints. Child participants are paired 1:1 with elderly in the intervention group; if an elderly participant drops out during the SHP phase, the paired child continues if feasible and

willing, or the session is adjusted accordingly without recruitment of new children. No over-recruitment or replacement strategy is employed to maintain the integrity of consecutive recruitment and randomization.

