4.5 Sample size calculation

The sample size was calculated to detect clinically meaningful differences between the intervention and control groups in key outcome measures, including handgrip strength, gait speed, cognitive function (MoCA-Ina score), health-related quality of life (SF-12), and serum mature brain-derived neurotrophic factor (mBDNF) levels.

Sample size estimation was performed using the formula for comparison of two independent means, with a two-sided significance level (α) of 5% and a statistical power ($1-\beta$) of 80%. The standard deviation and expected mean differences for each outcome were derived from previously published studies involving older adults, as no prior studies have specifically evaluated SHP-based interventions or their combination with structured physical exercise.

Based on these calculations, the required sample sizes for individual outcome parameters ranged from 9 to 42 participants per group. Considering the largest estimated sample size requirement and allowing for potential dropouts, the minimum required sample size for this randomized controlled trial was determined to be 100 older adult participants, with **50 participants allocated to each group (intervention and control)**.

This sample size is considered sufficient to evaluate the primary and secondary outcomes of the study and to ensure adequate statistical power while accounting for potential attrition during the study period.

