7. METHODS

7.1 Study parameters/endpoints

7.1.1 Main study parameter/endpoint

- Change in frailty syndrome status (assessed using Cardiovascular Health Study criteria: score 0 robust, 1–2 pre-frail, ≥3 frail) from baseline to week 16.
- Change in serum mature brain-derived neurotrophic factor (mBDNF) levels (measured by ELISA) from baseline to week 16.

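### No rule covers a missing week-16 frailty or mBDNF value, so the promised intention-to-treat analysis would by default use only people measured at week 16

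*Combined protocol and SAP*

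**What the plan says.** - **Endpoints.** Section 7.1.1 has two main endpoints, both changes to week 16: CHS frailty status, and "Change in serum mature brain-derived neurotrophic factor (mBDNF) levels (measured by ELISA) from baseline to week 16".
- **Drop-out.** Section 7.6 says the sample size "incorporates an anticipated drop-out rate of up to 15" percent, with no replacement. Section 7.5.1 counts as a drop-out anyone who does not complete the protocol through week 16. Its list includes poor session attendance as well as illness, voluntary withdrawal, loss to follow-up and death.
- **Follow-up after withdrawal.** For voluntary withdrawal, section 7.5 has "no further study procedures performed unless consented for final assessment". It then encourages withdrawn participants to have safety follow-up, final assessments or both. Section 7.7 says they are "encouraged to complete final assessments for intention-to-treat analysis where possible".
- **Analysis set.** Section 3 promises intention to treat, with per-protocol as the sensitivity analysis. Section 9 says: "Primary analyses will be conducted on the per-protocol (PP) population, excluding drop-out subjects".
- **Method.** Section 9 compares changes by unpaired t-test or Mann-Whitney U test. Its list of compared outcomes is grip strength, gait speed, MoCA-Ina, mBDNF and quality of life; frailty is not in it.
- **Week 12.** Sections 7.3.3 and 7.4 schedule a frailty assessment and a blood sample at week 12 for all participants. Section 9 does not use them.

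**The concern.** A change to week 16 does not exist for someone without a week-16 value. The plan foresees such people and does not replace them, but gives no imputation, no repeated-measures model, no rule for death and no missing-data sensitivity analysis. The only stated handling is exclusion.

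This gap is separate from the conflict between sections 3 and 9 over which population is primary. If that conflict were settled in favour of intention to treat, a t-test or Mann-Whitney test on change would still leave out anyone without a week-16 measurement. If losses are related to how participants are doing, or differ between arms, the comparison is no longer protected by randomisation. In an open-label trial, a missing-data rule chosen after the data are seen is also open to selection.

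**Working it through.** **1. The plan's own figure.** Inputs from section 4.5: a test "with a two-sided significance level (α) of 5" percent, 80% power, and "the required sample sizes for individual outcome parameters ranged from 9 to 42 participants per group". From section 7.6: 15% drop-out.

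- 42 / (1 − 0.15) = 49.4, rounded up to 50 per arm. The planned size reproduces.
- Standardised difference implied by 42 per arm: (1.960 + 0.842) × √(2/42) = 0.61 SD (0.62 from the t-test).
- At 0.61 SD, power is 86.4% with 50 per arm and 80.5% with 42.5 per arm.

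The inflation therefore covers lost precision. It does nothing about bias from who is lost. Section 4.5 says "The standard deviation and expected mean differences for each outcome were derived from previously published studies involving older adults" but shows neither, and does not say which outcome needed 42. So 0.61 SD cannot be called the planned mBDNF effect.

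**2. Drop-out is not the same as missing at week 16.** Section 5.1 plans 2×1 + 4×2 + 6×3 = 28 exercise sessions and 8 intergenerational sessions.

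- 85% of 28 is 23.8, so missing 5 exercise sessions makes a drop-out.
- Missing 2 of 8 intergenerational sessions leaves 6/8 = 75%, also below 85%.
- If each intergenerational session were attended independently with probability 95%, 90% or 85% (an assumption), the chance of missing 2 or more of 8 is 5.7%, 18.7% or 34.3%.

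Such people can still be measured at week 16, yet section 9 excludes them. Only the intervention arm has these sessions, so exclusions under the attendance criteria of 7.5.1 can arise only there.

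**3. Following one person through the text.**

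| Situation | Primary analysis (section 9) | Intention to treat (sections 3, 7.5, 7.7) |
|---|---|---|
| Non-adherent, attends week 16 | Excluded | Could be included |
| Withdrawn, returns for week 16 | Excluded | Could be included |
| Week-12 value, no week-16 value | Excluded | No rule; named tests omit the person |
| Neither value | Excluded | No rule; named tests omit the person |
| Died | Excluded | No rule |

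For frailty the gap comes earlier: section 9 names no between-arm comparison at all.

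**4. Illustration of bias (assumed, not from the documents).** Suppose 15% of the intervention arm is lost and nobody in the control arm. Loss falls on the highest 15% of a score equal to minus the standardised week-12 change plus independent unit-variance noise.

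- Mean standardised score among those kept: −φ(1.036)/0.85 = −0.233/0.85 = −0.274.
- The score has SD √2, so the mean week-12 change among those kept is too high by 0.274/√2 = 0.194 SD.
- Carried to week 16 with correlation 0.5: 0.194 × 0.5 = 0.097 SD. With 0.7: 0.194 × 0.7 = 0.136 SD.
- Against 0.62 SD these are 16% and 22%.

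Simulation agrees (0.098 to 0.137 SD). Using week-12 values for every drop-out brings the bias to about zero, and for half of them to about 0.05 to 0.06 SD. That recovery follows from the set-up, because loss was made to depend on week-12 change.

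**5. What week-12 data would not repair.** If 15% of the intervention arm dropped out and got no benefit, the all-randomised effect would be 0.85 × 0.61 = 0.52 SD, and completers would overstate it by 1/0.85 = 1.18, or 18%. A model that assumes missing-at-random does not correct this. Only a sensitivity analysis that departs from that assumption probes it.

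**The case against.** Several stronger readings are tempting, and the documents do not support them.

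- **A reader might infer that up to 15% will have no week-16 value.** The 15% is a drop-out allowance, and drop-out includes non-adherent people who can still be measured. The documents give no expected missing rate; it could be lower.
- **A reader might infer that intention to treat can only be a completer analysis.** Withdrawn participants who attend week 16 could be included. The default is an analysis of everyone with a week-16 value.
- **A reader might infer that the final assessment of a withdrawn person could be taken at the time of leaving.** Sections 3, 7.3, 7.4 and 7.5.1 all place the final assessment at week 16. A week-12 value already collected is not discarded either, since section 7.5 documents partial data. What is missing is a request that people who stop before week 12 attend that visit.
- **A reader might infer that most drop-out criteria bear on the intervention arm only.** Of the seven in section 7.5.1, five apply to both arms. Non-adherence is clearly specific to the intervention arm. Intervention-related adverse events lean that way, but section 8.1.1 counts education, assessments and blood sampling among the study interventions.
- **A reader might infer that the result will favour the intervention.** Nothing in the documents shows that poor responders leave more often; the examples given include lack of time, transport and acute illness. Step 4 puts all loss in one arm and is an extreme case.

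It can also be said that a mixed model with imputation is one acceptable package among several. That is fair. What stands is that the plan names none, and that its stated handling excludes randomised people whose data may be available.

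**Conclusion.** The point holds in this form. Section 9 excludes drop-outs from the primary analysis, and no section says how a missing week-16 frailty or mBDNF value is handled. The intention-to-treat analysis would by default rest on people with a week-16 value, and week-12 data in both arms would be left aside. Exclusions may be unbalanced because the attendance criteria concern sessions that only the intervention arm has.

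The share missing, and the direction and size of any bias, cannot be derived from the documents. The 0.10 to 0.14 SD figure depends on three assumptions: 15% loss in the intervention arm only, loss driven by poor week-12 change, and a week-12 to week-16 correlation of 0.5 to 0.7. It shows that a bias worth preventing is possible, not that one is expected. The change should be made before data are analysed, and the follow-up wording before participants start to leave, because values not collected cannot be recovered.

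**What to change.** **Section 9**

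- Analyse all randomised participants in the arm to which they were assigned.
- For mBDNF and the other continuous outcomes, use a mixed model for repeated measures on weeks 12 and 16 with baseline, arm, visit and arm-by-visit, and report the arm difference at week 16.
- For frailty, first name the between-arm comparison. Then use multiple imputation from baseline and week-12 status, with a stated rule for death.
- Add one delta-adjusted sensitivity analysis for departures from missing-at-random. It should cover people with neither a week-12 nor a week-16 value, who contribute nothing to the arm difference in the mixed model.

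**Sections 7.5 and 7.7**

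- State that people who stop the intervention or are classed as non-adherent, but have not withdrawn consent, are asked to attend the scheduled week-12 and week-16 assessments.

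**Cost.** Rewording of section 9 and a sentence in each of 7.5 and 7.7. The visits and blood samples are already planned. The analysis becomes slightly more complex, and the reported effect may be smaller.
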